## **EXECUTIVE SUMMARY**

This prospective, single-center, interventional study evaluated the efficacy of the **5-Line Principle of Balanced Intensity Training (BPIT)** in improving physical performance and reducing injury risk over a 6-week training period.

- **Participants:** Twenty-three participants (18 males aged 22-48 years, 5 females aged 20-33 years) completed the study with a mean adherence rate of 94.9%.
- **Key Findings:** The BPIT protocol demonstrated statistically significant improvements across all measured outcomes, including:
  - Strength gains of 15-25%.
  - Enhanced autonomic function (HRV increase of 12.67 ms).
  - Improved biomechanical efficiency (knee valgus reduction of 17.9%).
  - A low injury incidence rate of 4.3%.
- **Conclusion:** These findings support the BPIT method as an effective and safe training approach for diverse populations.

## **1. INTRODUCTION**

### **1.1 Background**

Traditional strength training often leads to plateaus, overtraining, and increased injury risk. The BPIT, developed by [name], cycles through five distinct levels of exercise intensity to optimize neuromuscular adaptation, enhance recovery, and minimize biomechanical stress.

- **Line 1:** Ground-Based, Low Intensity
- **Line 2:** Knee-Level, Low-Moderate Intensity
- **Line 3:** Standing, Moderate Intensity
- **Line 4:** Head-Level, Moderate-High Intensity
- **Line 5:** Plyometric/High-Impact, High Intensity

### **1.2 Study Rationale**

This study provides the first formal evaluation of the BPIT protocol in a structured research setting.

## 1.2 ClinicalTrials.gov & DOI

This study is registered on ClinicalTrials.gov under the identifier **NCT[pending]**. A Digital Object Identifier (DOI) will be assigned upon formal publication:

**DOI: [To be inserted post-registration]**. I.e. Zenodo DOI: 10.5281/zenodo.[pending]

## 1.3 Study Objectives

- **Primary Objective:** To assess the efficacy of the 6-week BPIT protocol in improving maximal strength (1RM) and reducing the incidence of training-related injuries.
- **Secondary Objectives:** To evaluate the impact on heart rate variability (HRV), heart rate recovery (HRR), muscle activation patterns (EMG), and joint biomechanics (knee valgus, spinal curvature).

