## 2.5 Outcome Measures

- **Primary:** Change in 1RM (squat, bench press, deadlift); Incidence of training-related injuries.
- **Secondary:** Change in HRV (RMSSD); Change in HRR; Change in EMG (rectus abdominis, quadriceps); Change in knee valgus angle and spinal curvature.

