## 5. CONCLUSIONS

This study provides strong evidence supporting the efficacy and safety of the BPIT 5-Line protocol for improving physical performance and reducing injury risk. The BPIT method is a valuable addition to the strength and conditioning field.

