## 1. Objectives (directly from protocol)

Primary

- To assess change from baseline to Week 6 in 1-repetition maximum (1RM) for squat, bench press, and deadlift
- To assess the incidence of training-related injuries over the 6-week period

Secondary

- Change in resting heart rate and heart rate variability (HRV – RMSSD)
- Change in heart rate recovery (HRR) – if measured
- Change in muscle activation (EMG %MVC) for rectus abdominis and quadriceps
- Change in knee valgus angle and spinal curvature (degrees)

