#### **4. Injury Incidence**

- Proportion of participants with  $\geq 1$  training-related injury (with 95% Clopper-Pearson exact CI)
- Injury rate per 1,000 training hours

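### The conclusion that the training reduces injury risk, and the listing of 4.3% injuries among significant improvements, have no comparator or test behind them: the study only estimates incidence

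*Protocol*

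**What the plan says.** **Objective.** Protocol section 1.3 includes efficacy in "reducing the incidence of training-related injuries" in the primary objective, alongside maximal strength.

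**Outcome and analysis.** The matching primary outcome in Protocol section 2.5 is "Incidence of training-related injuries", with no comparison attached. SAP section 1 words the objective as "To assess the incidence of training-related injuries over the 6-week period". SAP section 4 plans the proportion of participants with at least one "training-related injury (with 95% Clopper-Pearson exact CI"), and a rate per 1,000 training hours. SAP section 7 describes the study as exploratory and single-arm.

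**Result.** Protocol section 3.2.2 reports one mild muscle strain, given as 4.3% (1 of 23) and 2.54 per 1000 training hours. That text carries no interval.

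**Claims.** The Executive Summary opens its findings with "The BPIT protocol demonstrated statistically significant improvements across all measured outcomes", and one item in the list beneath is "A low injury incidence rate of 4.3"%. It concludes that the method is "an effective and safe training approach for diverse populations". The Discussion repeats the significance claim for every measured outcome and says that the injury figure supports safety. Section 5 concludes that there is "strong evidence supporting the efficacy and safety of the BPIT 5-Line protocol for improving physical performance and reducing injury risk".

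**Limitations.** Section 4.6 acknowledges the missing control group, the small sample and the short duration.

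**The concern.** A reduction is a comparison, and the supplied documents contain nothing to compare with. There is no control arm, no historical or target rate, and no pre-study period in which injuries were counted. The plan estimates an incidence, while the report concludes an effect.

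The significance listing has the same fault. Each continuous outcome has a baseline and a Week 6 value and a planned paired test. Injury has neither a baseline value nor a planned test, so it can be neither an improvement nor statistically significant under this plan.

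The words low and safe are also used without any statement of precision, although the SAP provides for one.

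Injury is one of the two primary outcomes. Someone who reads only the Executive Summary and the Conclusions would take away that the programme lowers injury risk and that this was tested.

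**Working it through.** **1. Inputs.**
- Injured participants x = 1 and participants n = 23 (Protocol section 3.2.2).
- Three 60-minute sessions a week for six weeks, so 3 × 1 h × 6 = 18 h per person (Protocol section 2.4).
- Mean adherence 94.9% (Protocol section 3.1).
- Two-sided 95% Clopper-Pearson interval (SAP section 4).

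**2. Reproduce the reported figures.**
- Proportion: 1/23 = 0.0435, which agrees with the stated 4.3%.
- Hours: 23 × 18 = 414 at full attendance; 414 × 0.949 = 392.9 attended.
- Rate: 1000 × 1/392.9 = 2.545 per 1000 h, against 2.54 stated. Rounding of the adherence figure can account for the difference: at 94.95%, 1000/(414 × 0.9495) = 2.544.

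The point estimates are sound. The fault is in what is inferred from them.

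**3. The planned interval.** With x = 1 and n = 23:
- Lower limit: the 0.025 quantile of Beta(1, 23), which equals 1 − 0.975^(1/23) = 0.00110, or 0.1%.
- Upper limit: the 0.975 quantile of Beta(2, 22) = 0.21949, or 21.9%.
- Check: the binomial probability of one or fewer injuries in 23 at a risk of 0.21949 is 0.025, as it should be.

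**4. The most favourable result possible.** With x = 0 and n = 23, the two-sided 95% upper limit is 1 − 0.025^(1/23) = 0.148. No result with 23 participants could have put that limit below 14.8%. A one-sided 95% limit would be 1 − 0.05^(1/23) = 0.122, but the SAP does not plan a one-sided limit.

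**5. Dependence on a comparator.** The documents give no reference risk, so the following values are assumptions used only to show the dependence. The probability of one or fewer injuries in 23 would be:

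| Assumed 6-week risk | P(0 or 1 injury in 23) |
|---|---|
| 5% | 0.68 |
| 10% | 0.32 |
| 15% | 0.12 |
| 20% | 0.040 |

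The same result looks ordinary or unusual depending wholly on a figure that the documents do not supply.

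**6. Claim against plan.** Protocol section 2.5 and SAP sections 1 and 4 all stop at estimation. Protocol section 5 and the Executive Summary go beyond it. No step in the supplied text connects the two.

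**The case against.** **The limitations are disclosed.** Section 4.6 states them directly before the Conclusions and calls for randomised trials. The SAP is also sound on this point: it restricts injury to estimation with an exact interval and calls the study exploratory. All of that stands, and it means the plan's analysis is not what is at fault. But section 5 does not carry the limits over to the injury claim, and an exploratory label makes a claim of strong evidence harder to defend.

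**The biomechanical results show lower injury risk.** Section 3.3.2 presents the fall in knee valgus angle and spinal curvature as a reduction in injury risk factors. These are pre-post changes in surrogates without a control group. They do not show that fewer injuries occurred.

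**The interval may exist elsewhere.** Appendix C names a statistical results file that was not supplied. A reader might infer that the planned interval was never calculated, but the documents do not support that. What can be said is that the text of section 3.2.2 lacks it. The captions of Figures 1 to 4 do not describe injury, and SAP section 10 lists only Tables 2 to 5 and Figures 1 to 4. If the interval is in the attachment, that settles the omission only; it supplies neither a comparator nor a test.

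**Only wording changes.** This is true: no estimate or dataset is altered. The missing interval taken alone would be a modest reporting gap. The reduction claim and the significance listing are more serious, because they state a conclusion on a primary outcome that the design cannot reach.

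**Conclusion.** The point holds. The supplied documents support a statement of incidence, 1 of 23 (4.3%, exact 95% interval 0.1% to 21.9%), and nothing about a reduction. Injury was not tested, so it does not belong among statistically significant outcomes. The lack of a comparator is decisive by itself and would remain so at any sample size. The width of the interval adds that low and safe rest on imprecise data.

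Two stronger readings are not supported. A reader might infer that the training is unsafe, or that the risk is about 22%. The interval runs down to 0.1% as well as up to 21.9%, and without a reference rate it argues neither for harm nor for benefit. A reader might also infer that the SAP's injury analysis is wrong; it is suitable for estimating incidence.

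The conclusion assumes that the attachments contain no reference rate or injury comparison, since they were not supplied. The interval assumes that the 23 participants are independent with a common risk, as the planned method does. No view is taken here on the tests of the continuous outcomes.

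**What to change.** 1. **Protocol section 5.** Delete the claim of reduced injury risk and remove the claim of strong evidence for safety. Write instead: *One of 23 participants was injured (4.3%, exact 95% CI 0.1% to 21.9%); the single-arm design could not test whether BPIT changes injury risk.*
2. **Executive Summary and section 4.** Move the 4.3% out of the list of significant findings to a line of its own. In both places, narrow the statement about every measured outcome so that it excludes injury, for example to *all tested continuous outcomes reported*. Moving the bullet alone would not be enough, because injury is itself a measured primary outcome. Give the interval beside the words low and safe and beside the Discussion's safety statement.
3. **Section 3.2.2.** Add the interval to 1/23, and keep the 2.54 per 1000 training hours, which the SAP also plans.
4. **Section 4.6.** State that the injury-reduction part of the objective could not be addressed and that only incidence was estimated. Leave the objective in section 1.3 on record as written.

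The cost is a few sentences and one interval that the SAP already plans; no new data are needed. The downside for the sponsor is a less favourable injury and safety message. To support a claim of reduction, a future study would need a control group or a reference rate justified in advance.

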# 2. METHODS

## 2.2 Participants

Twenty-three healthy adults were enrolled.

**Table 1: Participant Demographics**

Characteristic	Value
Total Participants	23
Males	18 (78.3%)
Females	5 (21.7%)
Mean Age <math>\pm</math> SD	35.2 $\pm$ 8.4 years
Mean BMI (Baseline) <math>\pm</math> SD	24.8 $\pm$ 3.1 $\text{kg/m}^2$

## 2.4 Intervention

The BPIT protocol involved three 60-minute sessions per week for six weeks. Each session progressed through the five intensity lines with auto-regulated rest intervals.

## 2.5 Outcome Measures

- **Primary:** Change in 1RM (squat, bench press, deadlift); Incidence of training-related injuries.
- **Secondary:** Change in HRV (RMSSD); Change in HRR; Change in EMG (rectus abdominis, quadriceps); Change in knee valgus angle and spinal curvature.

# 3. RESULTS

### 3.1 Participant Flow and Adherence

- All 23 enrolled participants completed the intervention.
- Mean adherence was 94.9%.

### 3.2 Primary Outcomes

[figure not shown]
#### 3.2.1 Strength Improvements

Strength gains ranged from 15% to 25%.

**Table 2: Strength Outcomes (1RM) - Mean Change (kg)**

Exercise	Baseline Mean ± SD (kg)	Week 6 Mean ± SD (kg)	Mean Change (kg)	Cohen's d
Squat	109.32±22.49	132.23±28.45	+22.91	3.44
Bench Press	76.57±21.11	92.68±25.87	+16.11	3.12
Deadlift	123.10±28.26	147.70±33.55	+24.60	4.01

Strength gains ranged from 15% to 25% across all exercises, with the deadlift showing the largest absolute improvement (24.60 kg) and the largest effect size (Cohen's d = 4.01). These results demonstrate the robust efficacy of the BPIT protocol in enhancing maximal strength.

**Figure 1:** Changes in 1-Repetition Maximum (1RM) for squat, bench press, and deadlift from baseline to Week 6. Individual participant data are shown as gray lines, with mean  $\pm$  SD represented by black error bars.

#### 3.2.2 Injury Incidence

Only one mild muscle strain was reported, resulting in an injury incidence rate of 4.3% (1/23 participants) and an injury rate of 2.54 per 1000 training hours.

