## 4. DISCUSSION

The BPIT protocol is highly effective, demonstrating statistically significant and clinically meaningful improvements across all measured outcomes, with large effect sizes ( $d$  ranging from 2.97 to 4.76). The low injury incidence rate (4.3%) supports its safety profile. The intensity cycling likely optimizes the balance between training stress and recovery, leading to enhanced adaptation.

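### The co-primary injury result rests on one strain and is reported with no interval, so it cannot show a low injury rate or a reduction in injury risk

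*Protocol*

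**What the plan says.** Protocol sections 1.3 and 2.5 make training-related injury a primary objective and a primary outcome alongside 1RM strength, and SAP section 1 repeats this.

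Report section 3.2.2 states the result: "Only one mild muscle strain was reported". It expresses this as 4.3% (1/23) and as "an injury rate of 2.54 per 1000 training hours". No interval accompanies either figure.

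SAP section 4 has two items. The first is the proportion of participants injured, with an exact Clopper-Pearson 95% interval. The second reads, in full, "Injury rate per 1,000 training hours"; it has no interval and no definition of the hours.

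On exposure, Protocol section 2.4 says "The BPIT protocol involved three 60-minute sessions per week for six weeks" and "Each session progressed through the five intensity lines with auto-regulated rest intervals". Section 3.1 adds "All 23 enrolled participants completed the intervention" and gives mean adherence of 94.9%.

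On interpretation, the Discussion says "The low injury incidence rate (4.3%) supports its safety profile". The Conclusions describe the evidence as strong for efficacy and safety and for lower injury risk. Section 4.6 acknowledges that there was one arm, no control group and 23 participants.

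**The concern.** Both injury figures come from the same single event. A rate given to two decimals, or a proportion of 4.3%, looks like a settled estimate when nothing beside it shows how little information lies behind it. One event cannot separate a very low injury rate from a fairly high one.

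The gap arises in two places. The plan never asks for an interval on the hourly rate. For the proportion it does ask, and the report does not deliver. The list of outputs in SAP section 10 (Tables 2 to 5, Figures 1 to 4) covers strength, physiology, biomechanics and EMG. None of these outputs is for injury, so the planned interval has no assigned place.

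At stake is half of the primary objective. The conclusions on safety and on reduced injury risk are stated firmly, and a reader has no means of seeing that the data do not carry them.

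**Working it through.** **Inputs.** Events: 1 (report section 3.2.2). Participants: 23, all completers (section 3.1). Schedule: 3 sessions a week for 6 weeks, 60 minutes each (section 2.4). Mean adherence: 94.9% (section 3.1).

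**Step 1: reproduce 2.54.** Rate = 1,000 × events / hours.

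- Scheduled sessions: 23 × 3 × 6 = 414, or 414 h at 60 minutes each. 1,000 × 1/414 = 2.42, which does not match.
- Attended sessions: every participant has the same 18 scheduled sessions, so mean adherence equals pooled attendance. 392/414 = 94.7%, 393/414 = 94.9% and 394/414 = 95.2%, so 393 is the only whole number that fits.
- 393 sessions × 1 h = 393 h. 1,000 × 1/393 = 2.5445, which rounds to 2.54 and matches.
- Any total from 1,000/2.545 = 392.9 h to 1,000/2.535 = 394.5 h also rounds to 2.54. The match strongly suggests attended sessions at nominal length but does not prove it.

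**Step 2: exact Poisson 95% interval for the rate.** For one observed event, the limits on the expected count are:

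- Lower: solve 1 − exp(−μ) = 0.025, so μ = −ln(0.975) = 0.0253.
- Upper: solve exp(−μ)(1 + μ) = 0.025, so μ = 5.572.

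Divided by 393 h: 1,000 × 0.0253/393 = 0.06 and 1,000 × 5.572/393 = 14.2 per 1,000 h. The upper limit is 5.572 times the point estimate, about 5.6.

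**Step 3: Clopper-Pearson 95% interval for 1/23.**

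- Lower: 1 − 0.975^(1/23) = 0.0011, or 0.1%.
- Upper: solve (1 − p)^23 + 23p(1 − p)^22 = 0.025, so p = 0.219, or 21.9%.

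**Step 4: does the undefined denominator matter?** The documents give no active training time. The shares below are assumptions.

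| Assumed active share of the hour | Rate per 1,000 h | Upper 95% limit |
|---|---|---|
| 100% (nominal) | 2.54 | 14.2 |
| 90% | 2.83 | 15.8 |
| 75% | 3.39 | 18.9 |
| 50% | 5.09 | 28.4 |

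Halving the hours doubles the rate to 5.09, which is still well inside 0.06 to 14.2. The single event is the main source of uncertainty; the definition of hours is secondary.

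**The case against.** Section 3.2.2 hides nothing: the same sentence gives the single strain and 1/23, so a careful reader can see how thin the data are. The SAP calls the study exploratory, and section 4.6 concedes the small sample and the absence of a control. Adding intervals would not move either point estimate. The report also refers to attached data and results files that are not part of these documents; they may contain the denominator or an interval.

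Much of this is fair as description. It does not answer the point, because the Discussion and Conclusions go beyond describing one event, and a limitation stated in one section does not qualify a firm claim in the next.

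Four stronger readings are tempting, and the documents do not support them.

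- *The safety claim rests on 2.54.* It does not. The Discussion cites the 4.3%, and the hourly rate appears only in section 3.2.2. The weakness applies to both figures, and most directly to the 4.3%.
- *The denominator is known to be nominal time.* This is a close inference from the arithmetic. Neither document states the denominator.
- *Pooling rest and low-intensity work with plyometric work invalidates the rate, so injuries must be reported by intensity line.* The intervention is the whole session through all five lines, and no objective or SAP item promises safety by line. One event could not inform such a breakdown, and no session logs by line are described.
- *The wide interval suggests the programme is unsafe.* It does not. The interval also includes very low rates.

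**Conclusion.** The point holds. One strain in about 393 session-hours gives 2.54 per 1,000 h with an exact 95% interval of 0.06 to 14.2. One injured participant in 23 gives 4.3% with an exact 95% interval of 0.1% to 21.9%. Neither interval appears in section 3.2.2, and only the second was planned. Data compatible with an injury to about one participant in five over six weeks do not establish a low rate. Without a comparator they cannot show a reduction in risk at all, however narrow the interval.

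The rate interval assumes 393 h of exposure and a constant Poisson rate. If the true denominator differs, the limits scale in inverse proportion. The interval for the proportion needs only the 1 and the 23. The undefined hours are a lesser matter of labelling.

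**What to change.** - **SAP section 4:** add an exact Poisson 95% interval for the hourly rate and define the hours. The SAP refers to a final report that already exists, so mark this as added after the results were known.
- **Report section 3.2.2:** give both exact intervals (0.06 to 14.2 per 1,000 h; 0.1% to 21.9%) and state the denominator. If the study data confirm it, describe it as 393 attended sessions at a nominal 60 minutes, rest included. Otherwise recompute on the confirmed hours.
- **Discussion and Conclusions:** replace the statements that the low rate supports safety, and that there is strong evidence of safety and lower injury risk. Say instead that one injury was observed, that the data are compatible with a rate of up to about 14 per 1,000 session-hours or about 22% of participants, and that without a control group no reduction can be inferred. Bring the matching lines of the Executive Summary into agreement.

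The cost is two intervals, one check of the denominator and some rewording, with no new data. The downside for the sponsor is that the safety figures will read less favourably.

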### 3.3 Secondary Outcomes

### 3.3.1 Physiological Improvements

The decrease in resting heart rate (6.02 bpm) and increase in HRV (12.67 ms) indicate enhanced autonomic function.

**Table 3: Physiological Outcomes**

Measure	Baseline Mean ± SD	Week 6 Mean ± SD	Mean Change	Cohen's d	p-value
Resting Heart Rate (bpm)	67.96 ± 9.20	61.93 ± 9.58	-6.02	-4.01	<0.001
HRV RMSSD (ms)	44.25 ± 11.05	56.93 ± 10.21	+12.67	4.76	<0.001

**The decrease in resting heart rate (6.02 bpm) and increase in HRV (12.67 ms) indicate enhanced autonomic function and improved cardiovascular efficiency. These findings align with the recovery-focused design of the BPIT protocol.**

[figure not shown]

Figure 2: Changes in resting heart rate and heart rate variability from baseline to Week 6. Individual participant data are shown as gray lines, with mean  $\pm$  SD represented by black error bars.

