#### **5. Secondary Efficacy Analyses**

All continuous secondary endpoints analysed exactly as primary (paired t-test/Wilcoxon, Cohen's d, 95% CI)

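### Table 3 text claims better cardiovascular efficiency and a link to recovery that no reported outcome measures, and reads two coupled quantities, resting heart rate and raw RMSSD, as joint support for better autonomic function

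*Protocol*

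**What the plan says.** Protocol section 3.3.1 and the text under Table 3 interpret two changes together: "The decrease in resting heart rate (6.02 bpm) and increase in HRV (12.67 ms) indicate enhanced autonomic function". The text under Table 3 goes further and says that they "indicate enhanced autonomic function and improved cardiovascular efficiency. These findings align with the recovery-focused design of the BPIT protocol". The Discussion (section 4) offers a mechanism: "The intensity cycling likely optimizes the balance between training stress and recovery, leading to enhanced adaptation". The Executive Summary repeats the autonomic conclusion and cites the raw RMSSD increase for it.

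The outcomes behind these statements are few. Protocol section 2.5 lists "Change in HRV (RMSSD); Change in HRR" among the secondary outcomes, and section 1.3 names the same two. SAP section 1 adds resting heart rate and makes heart rate recovery conditional: "Change in heart rate recovery (HRR) – if measured". For the analysis, SAP section 5 has "All continuous secondary endpoints analysed exactly as primary", so each endpoint gets its own paired test on its own scale.

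**The concern.** There are two separate problems.

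**Conclusions without a measure.** Resting heart rate and resting RMSSD, each taken at baseline and Week 6, do not measure cardiac output or work per beat, and they do not measure recovery after or between sessions. A reader of Table 3 would nevertheless take away that cardiovascular efficiency improved and that the results fit a recovery-based design.

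**Coupled readings.** RMSSD is the root mean square of successive differences between RR intervals, in ms. If every interval is multiplied by a factor, RMSSD is multiplied by the same factor. A slower heart rate can therefore raise RMSSD with no change in relative variability. Neither document plans or reports a heart-rate-corrected RMSSD or an adjustment for heart rate, so the planned analysis cannot show how much of the RMSSD rise goes beyond the fall in heart rate.

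At stake is the physiological conclusion, which reaches the Executive Summary.

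**Working it through.** **Inputs (protocol Table 3, n = 23).** Resting heart rate: 67.96 ± 9.20 to 61.93 ± 9.58 bpm, stated change -6.02, d = -4.01. RMSSD: 44.25 ± 11.05 to 56.93 ± 10.21 ms, stated change +12.67, d = 4.76. Both p-values are given as <0.001.

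**Step 1: reproduce the table.**
- Changes: 61.93 - 67.96 = -6.03 and 56.93 - 44.25 = +12.68. Both agree with the stated values within rounding.
- SD of change = |change|/|d|: 6.02/4.01 = 1.50 bpm and 12.67/4.76 = 2.66 ms.
- |t| = |d| × √23: 19.2 and 22.8 on 22 df. Both p-values are far below 0.001.

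The rows are therefore consistent with a paired d and the stated p-values. The problem lies in the interpretation.

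**Step 2: compare conclusions with outcomes.**

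| Statement | Outcome listed | Result reported |
|---|---|---|
| Cardiovascular efficiency (Table 3 text) | None in protocol 1.3 or 2.5, or SAP 1 | None in Tables 2–5 |
| Recovery (Table 3 text, Discussion) | Heart rate recovery in protocol 1.3 and 2.5; conditional in SAP 1 | None in Tables 2–5 or the text |
| Autonomic function (Executive Summary, 3.3.1, Table 3 text) | RMSSD in both documents; resting heart rate in SAP 1 | Yes, raw scale only |

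Efficiency is mentioned elsewhere only for knee valgus (Executive Summary) and for EMG (section 3.3.3 and Table 5). Section 4.6 (Limitations) mentions neither gap.

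**Step 3: size of the coupling.**
- Mean RR = 60000/heart rate: 60000/67.96 = 882.9 ms and 60000/61.93 = 968.8 ms. Ratio 1.0974.
- RMSSD expected from heart rate alone = 44.25 × 1.0974^k. The exponent k is an assumption. k = 1 means constant relative variability, and 0.5 to 2 is shown as a range because the documents give no value.

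| k | Expected RMSSD (ms) | Rise from heart rate (ms) | Share of 12.67 | Remainder (ms) |
|---|---|---|---|---|
| 0.5 | 46.35 | 2.10 | 17% | 10.58 |
| 1 | 48.56 | 4.31 | 34% | 8.37 |
| 1.5 | 50.87 | 6.62 | 52% | 6.06 |
| 2 | 53.29 | 9.04 | 71% | 3.64 |

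- Exponent needed to explain the whole rise: ln(56.93/44.25)/ln(1.0974) = 2.71.
- RMSSD/RR: 44.25/882.9 = 5.01% and 56.93/968.8 = 5.88%, a relative rise of 17%. Raw: 56.93/44.25 = 1.287, a rise of 29%.

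**Step 4: do group means mislead?** The SD of the heart rate change implies a within-person correlation of (9.20² + 9.58² - 1.50²)/(2 × 9.20 × 9.58) = 0.988. Simulating normally distributed heart rates with these values gives a mean individual RR ratio of 1.101, against 1.097 from group means. The approximation is adequate for the RR ratio. The individual RMSSD split still needs the participant data.

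**The case against.** The strongest reply is that the conclusion on autonomic function survives. At k = 1 about two thirds of the RMSSD rise remains, and the corrected ratio still goes up. This stands. A reader might infer that heart rate explains the RMSSD change, but that would need an exponent of about 2.7, beyond the range assumed here, and the documents do not support it.

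Second, the one-third figure depends on a model. It needs k = 1, and it needs the resting heart rate in Table 3 to apply during the RMSSD recording. The documents describe no recording conditions and do not say that the two values share a recording. This also stands, so the size is given as a range.

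Third, raw RMSSD is the named secondary endpoint, and SAP section 5 analyses it as named. The SAP is dated 30 November 2024, the same day as primary completion, and its section 10 refers to a final report that already exists. Putting a derived ratio in place of the named endpoint now would favour an analysis chosen after the results were known. This stands too and limits the fix to a labelled sensitivity row.

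Fourth, the recovery wording is hedged. The Table 3 text says only that the findings fit the design, and the Discussion says likely. A reader might infer a claim that recovery was measured and improved, or that the two rows were presented as statistically independent or as proof of a vagal effect. The documents say none of this. The reference list also includes an article on heart rate variability and recovery in athletes, but neither document defines RMSSD as a recovery outcome. The hedging softens the recovery point without supplying a result. The efficiency claim carries no such hedge.

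Finally, these are secondary outcomes in an uncontrolled study, as section 4.6 acknowledges. Even a corrected change could not be attributed to the training. That limits the importance of the point, but the edits are small.

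**Conclusion.** The point holds in two parts of different strength.

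The first part rests on the documents alone. The cardiovascular efficiency conclusion has no outcome behind it. The recovery statements have no reported recovery measure behind them, because heart rate recovery is listed, then made conditional, and never reported.

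The second part is a qualification. The two rows of Table 3 are coupled and should not be read as separate support for better autonomic function. Slower heart rate alone would account for about +4.3 ms of +12.67 ms under proportional scaling, with an assumed range of +2.1 to +9.0 ms. This rests on group means, an assumed exponent and comparable recordings. It reduces the relative rise from 29% to about 17%. It does not show that the autonomic statement is wrong.

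**What to change.** 1. Delete the cardiovascular efficiency claim from the text under Table 3.
2. Report the heart rate recovery result, or state that it was not measured. State in the Discussion that the stress and recovery mechanism was not tested in this study.
3. Keep raw RMSSD as the named secondary endpoint. Beside it in Table 3, add a row labelled as a post hoc sensitivity analysis: each participant's RMSSD divided by that participant's mean RR interval from the same recording, with the same paired test and a 95% CI. If heart rate from that recording was not kept, say so and do not mix recordings.
4. State in the Executive Summary, section 3.3.1 and the Table 3 text that part of the RMSSD rise may reflect the lower heart rate.

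The cost is one derived variable, provided that the participant file listed in Appendix B holds both values, plus one table row and a few edited sentences. No new data are needed. The downside is a smaller and more qualified RMSSD effect.
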